### 6.10.2. Additional Analyses of the Primary Outcome

There are no additional analyses planned for the primary outcome.

### 6.10.3. Secondary Efficacy Analyses

Secondary efficacy analyses common to all ISAs within H0P-MC-CPMP have been described in the H0P-MC-CPMP SAP Version 5. H0P-MC-OA01 will also consider the following secondary analyses.

The Western Ontario and McMaster Universities Osteoarthritis Index (WOMAC®) is a validated instrument that is extensively used to evaluate the response to medications for the treatment of osteoarthritic pain. The WOMAC Version LK3.1 will be administered according to the Schedule of Activities.

This table describes the 24-question WOMAC and subscales.

Dimensions/Subscales	Number of Questions
Pain	5
stiffness	2
physical function	17

The participants will record their responses using a 0 to 4 Likert scale for each question:

- 0 = no pain, and
- 4 = extreme pain.

The scores for each subscale will be calculated by summing the scores of the questions in the respective subscale for each participant at each time point.

The range of possible scores for each subscale is pain = 0 to 20, stiffness = 0 to 8, and physical function = 0 to 68.

**Key Secondary Analysis**

A Bayesian longitudinal mixed-model repeated measures analysis (MMRM) will be performed to evaluate the change from baseline to each post baseline visit for the WOMAC® pain subscale, physical function subscale, and stiffness subscale. The model will utilize the constrained cell means model so that a common mean is estimated at the baseline. More details on this approach are provided in the H0P-MC-CPMP SAP Version 5.

This table describes information included in the model.

Categorical factors	
 
• the interaction of treatment and timepoint (constrained to estimate a common mean at baseline across treatments)
 
• average baseline pain severity category (baseline NRS < 7, baseline NRS >= 7)
 
• pooled investigative site
 

Continuous covariates	
 
• none
 

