1.1. Synopsis

Protocol Title:

Randomized, placebo-controlled, Phase 2 clinical trial to evaluate LY3016859 for the treatment of osteoarthritis

Rationale:

The purpose of this study is to test whether LY3016859 is efficacious in relieving knee pain due to osteoarthritis (OA). LY3016859 is a high affinity humanized immunoglobulin G (IgG)₄ monoclonal antibody that binds to key residues in the C-terminal regions of transforming growth factor- α (TGF- α) and epiregulin, preventing their binding to the epidermal growth factor receptor (EGFR).

Data will be collected to assess the safety, and tolerability of LY3016859 in this study population. Pharmacokinetic (PK) properties, pharmacodynamic (PD) effects and immunogenicity profile will also be explored. The totality of data from this proof-of-concept study will assess the benefits and risks associated with LY3016859 and inform decisions for the clinical development of LY3016859.

Objectives and Endpoints

The primary and secondary objectives and endpoints are stated in the master protocol H0P-MC-CPMP (CPMP) and OA disease-state addendum (DSA; H0P-MC-CPMP[1]).

Overall Design

This is a 26-week, Phase 2, randomized, double-blind, placebo-controlled study that will compare LY3016859 versus placebo in participants with OA in the knee.

Disclosure Statement: This is a randomized, investigator- and participant-blind, placebo-controlled, Phase 2 clinical trial.

Number of Participants:

Approximately 125 participants will be randomly assigned to study intervention (84 LY3016859 and 41 placebo) with the assumption that 15% of the participants will drop out prior to the end of the double-blind treatment period.

Intervention Groups and Duration:

This 26-week study includes an 8-week double-blind treatment period and an 18-week follow-up period.

[figure not shown]
Participants will receive an intravenous (IV) infusion every 2 weeks for a total of 4 infusions.

Intervention Name	LY3016859	Placebo
Dosage Level(s)	750 mg starting dose 500 mg subsequent doses	Not applicable
Route of Administration and duration	1 hour IV infusion	1 hour IV infusion

Participants will be monitored for at least 4 hours after completion of each infusion.

Data Monitoring Committee: Yes

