### 5.2. Determination of Sample Size

Approximately 125 participants will be randomized in a 2:1 ratio to LY3016859 or placebo, respectively. It is expected that approximately 107 participants will complete the double-blind treatment period of the study. CCI

If there is no treatment difference between placebo and LY3016859, the probability of passing the efficacy criterion specified above (i.e., false positive) is approximately 0.1. The simulation for the power calculation and sample size determination was carried out in FACTS Version 6.0.

CCI

If there is no treatment difference between placebo and LY3016859, the probability of passing the efficacy criterion specified above for average pain intensity (i.e., false positive) is approximately 0.1.

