## 8. Reports to be Generated at Final Database Lock

The following analysis will be performed for final database lock.

- Patient disposition - the analysis of patient disposition conducted in POC lock will be conducted for double-blind treatment and safety follow-up period combined.
- eCOA compliance - the overall eCOA compliance analysis conducted in POC lock will be summarized for the PDEP period plus at each nominal week up to Visit 801.
- Concomitant therapy – the analysis conducted in POC lock will be repeated including safety follow up period combined (may also include PDEP) except the listing of rescue medication use above protocol specified limits.
- Efficacy endpoint – The weekly average pain intensity via NRS will be calculated with extension to week 12 (Visit 801). The following analysis will be conducted across all time points in the double-blinded treatment and safety follow-up period combined (DB plus FU) based on the same model conducted in DB treatment period only.
  - Change from baseline in average pain intensity measured by weekly average of NRS
  - Change from baseline in worst pain intensity measured by weekly average of NRS
  - Change from baseline in DSA-specific physical functioning measures
  - Proportion of participants with a pain reduction from baseline greater than or equal to 30%, 50%, and 70% as measured by the average pain responses on the NRS
  - Proportion of participants with reduction from baseline greater than 30%, 50%, and 70% on DSA-specific physical function subscale
  - Overall improvement as Measured by Patients' Global Impression of Change (PGI)

A frequentist MMRM analysis will be conducted as a sensitivity analysis for the primary and some secondary endpoints.

A Bayesian MMRM subgroup analysis of baseline pain severity ( $<7$ ,  $\geq 7$ ) will be also evaluated for the primary and key secondary endpoint. A frequentist MMRM analysis will be performed as a sensitivity analysis for subgroup analysis.

- Safety analyses for TEAEs – the following analysis will be repeated including double-blind and safety follow-up period unless otherwise specified.
  - Overview of adverse event
  - SAE and a listing of SAE

- TEAE and Post-treatment emergent adverse event (PTEAE) by PT, by PT within SOC. A listing of TEAE and PTEAE will be provided.
- Post-treatment emergent AE by PT, by PT within SOC for safety follow-up period only
- Adverse event of special interest (ISA specific)

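### The constrained key secondary model lists baseline pain severity without a timepoint interaction, which forces equal mean change in both severity classes and can cost some precision at Week 8

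*SAP*

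**What the plan says.** SAP 6.10.3, Key Secondary Analysis, plans a Bayesian MMRM for the WOMAC pain, physical function and stiffness subscales. It uses a constrained cell means form, so baseline is a modelled timepoint with one mean shared by the arms. The table of model terms has three categorical factors and no continuous covariates:

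- "the interaction of treatment and timepoint (constrained to estimate a common mean at baseline across treatments"
- "average baseline pain severity category", split at a baseline NRS of 7
- pooled investigative site.

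Only the first is written as an interaction with time. The section refers to the master SAP (Version 5) for more detail on the approach, and SAP 6.2 refers there for covariate adjustment in general. The revision history says Version 3 added the constrained-model details to this section.

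On size, the SAP states "Approximately 125 participants will be randomized in a 2:1 ratio to LY3016859 or placebo, respectively", and the Protocol synopsis gives the split as "84 LY3016859 and 41 placebo". SAP Section 8 separately plans "A Bayesian MMRM subgroup analysis of baseline pain severity" for the primary and key secondary endpoints.

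**The concern.** In a conventional MMRM, baseline sits on the right-hand side, and a severity main effect shifts every post-baseline mean. Here baseline is also an outcome. A single severity coefficient therefore applies at baseline and at all later visits, and it drops out of any change from baseline. The model cannot let the two classes improve by different numbers of points.

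The classes are defined by pain measured at baseline, so regression to the mean would tend to narrow their WOMAC gap later. So would a roughly proportional response. A single coefficient is then a compromise between a large early gap and a small late one. At stake are the precision of the Week 8 difference and how well a chance imbalance in severity is corrected, which is the purpose of the covariate.

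**Working it through.** **The plan's own figures.** With "with the assumption that 15% of the participants will drop out prior to the end of the double-blind treatment period", 125 × 0.85 = 106.25, against the stated 107; 107 / 0.85 = 125.9. A 2:1 split of 125 is 83.3 to 41.7, against 84 to 41. These agree to rounding. The efficacy criterion, effect size and SD are redacted, so neither the power nor the false-positive figure of about 0.1 can be recomputed.

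**The model as listed.** Let T be treatment, S the severity class and j the timepoint:

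E[Y_j] = μ_j + τ_j·T + β·S + site, with τ_0 = 0.

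Then E[Y_8 − Y_0] = μ_8 − μ_0 + τ_8·T. Both β·S and site drop out. The estimate of τ_8 still depends on β: it adjusts for severity imbalance with coefficient β(1 − b), where b is the fitted slope of Week 8 on baseline.

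**Variance.** Assume:

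- g_j is the true WOMAC gap between severity classes at timepoint j
- Σ is the within-class covariance
- half of the participants are in each class
- randomisation is not stratified by severity
- data are complete and the sample is large.

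The fitted common coefficient is β = 1′Σ⁻¹g / 1′Σ⁻¹1. The residual covariance is R = Σ + 0.25(g − β)(g − β)′. Var(τ_8) is proportional to R_88 − R_80²/R_00. The crossed model replaces R by Σ; no covariate sets β = 0.

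**Worked case** (assumed: SD 3, all correlations 0.3, three timepoints, gap 3 at baseline and 1 later):

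- β = (3 + 1 + 1)/3 = 1.67.
- R_00 = 9 + 0.25 × 1.333² = 9.444; R_80 = 2.7 − 0.25 × 1.333 × 0.667 = 2.478; R_88 = 9 + 0.25 × 0.667² = 9.111.
- Main effect: 9.111 − 2.478²/9.444 = 8.461.
- Crossed: 9 − 2.7²/9 = 8.190.
- No covariate: 9.25 − 3.45²/11.25 = 8.192.
- Main effect against crossed: 8.461/8.190 = 1.033. This is worth 125 × (1 − 1/1.033) ≈ 4 participants.
- Imbalance: b = 2.478/9.444 = 0.262, so β(1 − b) = 1.23. The correct coefficient is 1 − 0.3 × 3 = 0.10. The uncorrected part per unit of imbalance is (1 − 1.667) − 0.262 × (3 − 1.667) = −1.02. A 10-point imbalance in the severe share is about 1 SD, since √(0.25 × (1/84 + 1/41)) = 0.095. It leaves an error of about 0.10 WOMAC points, against about 0.01 with no covariate.

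**Range** (assumed: SD 3, baseline-to-Week 8 correlation 0.3 to 0.5, two, three or five timepoints, two correlation patterns):

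| Gap at baseline → later | Main effect / crossed | Main effect / no covariate |
|---|---|---|
| 2 → 1 | 1.01–1.02 | 1.00–1.02 |
| 2 → 0.5 | 1.01–1.05 | 1.01–1.04 |
| 3 → 1 | 1.02–1.08 | 1.02–1.07 |
| 3 → 0 | 1.05–1.18 | 1.03–1.10 |
| 2 → 2 | 1.00 | 0.95–0.97 |
| 3 → 3 | 1.00 | 0.90–0.94 |

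If the SD instead rises from 2.5 at baseline to 4 later, the 3 → 0 case reaches 1.20 against crossed and 1.12 against no covariate.

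**Simulation of the worked case at 84:41.** Over 1,000 complete-data trials, the empirical SEs were 0.547 (main effect), 0.541 (crossed) and 0.539 (none). Main effect against crossed is (0.5473/0.5410)² = 1.02. The mean estimate was −0.996 under all three models. With 15% dropout (600 trials), the SEs were 0.6221 and 0.6207, a ratio of 1.005.

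**The case against.** The strongest reply is that the table may not be the full parameterisation. SAP 6.10.3 and 6.2 both defer to a master SAP that may cross covariates with time. That stands as a condition on the point. If the master SAP does so, all that is needed is a clarifying phrase.

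The size also depends entirely on assumed inputs. With a constant gap, the main effect is as good as the crossed term and better than no covariate. That stands too.

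Randomisation may be stratified by severity in the master design; Protocol 6.3 says only that this appendix adds no factors. Stratification would remove most of the real loss. In the worked case the actual variance term becomes 9 − 2 × 0.262 × 2.7 + 0.262² × 9 = 8.20, close to 8.19. The model would still report about 8.46, so the interval would be slightly too wide.

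Four stronger readings are tempting, and the documents do not support them:

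- **The covariate has no effect.** It cancels from modelled mean change only; it still moves the treatment estimate through β(1 − b).
- **The treatment effect is biased.** Under randomisation it is not; mean estimates matched the simulated effect within simulation error.
- **The sponsor itself expects change to differ by severity.** The Section 8 subgroup asks whether the treatment effect differs by severity, and planning it states no expectation.
- **Dropout makes matters worse.** With an unstructured covariance, dropouts are predicted from their own earlier scores as well, and the one simulation with dropout showed a smaller loss.

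**Conclusion.** The point holds as a modest, inexpensive improvement to the key secondary analysis. On the text of SAP 6.10.3, mean change to Week 8 is constrained to be equal in the two severity classes. If the gap narrows but does not close, the variance cost against the crossed model is typically 1 to 7%. If a 3-point gap closes completely, it reaches about 18% with a constant SD of 3, and about 20% if the SD also rises after baseline. In these large-sample calculations the crossed model was never less precise than the main effect or no covariate.

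The conclusion rests on the table being the full factor list and on assumed values for the SD, correlations, severity split, gaps and number of WOMAC visits, none of which the available documents give. It covers the continuous WOMAC models, including their extension through follow-up in SAP Section 8. The responder models use post-baseline observations only, so the cancellation does not arise there.

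**What to change.** In the SAP 6.10.3 table, replace the severity entry with baseline pain severity category by timepoint, or state that the master SAP (Version 5) already includes this term. Pooled site cancels by the same algebra, so treat it the same way if the number of pooled sites allows.

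Timing matters. The revision history places Version 3 before the proof-of-concept unblinding and Version 4 before the final lock. If the proof-of-concept data have been unblinded, keep the specified model as the key secondary analysis and report the crossed model as a labelled sensitivity analysis.

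The cost is one extra coefficient per post-baseline visit, and no new data. In the 84:41 simulation with a constant 3-point gap, where crossing gains nothing, it raised the variance by about 1%: (0.5467/0.5432)² = 1.013.

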**Other Secondary Analysis**

The proportion of participants in each treatment group meeting pre-specified binary response thresholds will be calculated for each post baseline time point and will be used to compare treatment groups.

The prespecified binary response thresholds for WOMAC® pain and function subscales are 30%, 50%, and 70%.

A Bayesian pseudo-likelihood-based categorical repeated measures regression model that includes all post baseline observations will be used to estimate the probability of achieving the response level in each treatment group and will be used to compare treatment groups.

The model will include the categorical and continuous covariates described for the key secondary analysis.

In addition, time to first treatment response from baseline based on the prespecified binary thresholds above will be assessed. Analyses will be conducted according to the time to event analyses specified in the CPMP SAP Version 5.

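### The WOMAC responder model takes its covariate list from the key secondary MMRM and so, in the supplied documents, has no baseline WOMAC term: a minor gap with a cheap remedy

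*SAP*

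**What the plan says.** SAP Section 6.10.3 sets out two kinds of model for the WOMAC subscales.

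- **Key secondary analysis.** This is a Bayesian MMRM for change from baseline. "The model will utilize the constrained cell means model so that a common mean is estimated at the baseline". Its table of terms has three categorical factors: treatment by timepoint (with the baseline constraint), a baseline NRS category split at 7, and "pooled investigative site". The row headed "Continuous covariates" has the entry none.
- **Other secondary analysis.** Response at the 30%, 50% and 70% thresholds is analysed with "A Bayesian pseudo-likelihood-based categorical repeated measures regression model that includes all post baseline observations". On covariates the SAP says only: "The model will include the categorical and continuous covariates described for the key secondary analysis".

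Three other places matter. Section 6.2 leaves the general covariate strategy to the master SAP. Section 6.10.3 leaves time to first response to the master SAP as well. Section 8 extends the efficacy analyses to Week 12, using the model already fitted for the double-blind period.

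**The concern.** An empty continuous row is coherent in the key secondary model. There baseline WOMAC is part of the outcome vector, and its correlation with the later scores does the work of a covariate. The responder model contains no baseline observation, so the same list does a different job. Baseline WOMAC then enters only as the denominator of percent reduction, which is not covariate adjustment. The NRS category is a different instrument cut into two levels, and it is a more distant proxy for physical function than for pain.

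Two things are at stake:

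- A chance difference between arms in baseline WOMAC can move the estimated responder difference, at three thresholds and every post-baseline visit.
- The borrowed list cannot be applied literally. It asks for continuous covariates from a list that has none, and for a baseline constraint in a model with no baseline time point. The programmer would have to improvise.

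**Working it through.** **The plan's own figures.** The protocol synopsis gives 125 randomised (84 and 41) and 15% dropout. Then 125 × 0.85 = 106.25, and 107 / 0.85 = 125.9. Both agree with the stated 107 completers and 125 randomised, to rounding. By arm, 84 × 0.85 = 71.4 and 41 × 0.85 = 34.9. Effect size, SD and success criterion are redacted, so power cannot be reproduced. No stated figure is wrong.

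**Terms side by side.**

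| Term | Key secondary MMRM | Responder model as written |
|---|---|---|
| Baseline WOMAC | modelled time point | absent |
| Treatment by timepoint | common mean at baseline | constraint has no counterpart |
| Baseline NRS category | yes | yes |
| Pooled site | yes | yes |
| Continuous covariate | none | none |

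**Assumed inputs (not in the documents).** 72 and 35 completers; baseline WOMAC pain mean 11, SD 2.8; correlation with NRS 0.5; a 2-point drug effect (risk difference about 0.20); slope of Week 8 score on baseline 0.2 to 0.8. The model is a single-visit logistic regression, simpler than the planned one.

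**Size of a chance imbalance.** One SD of the difference in baseline means is 2.8 × √(1/72 + 1/35) = 2.8 × 0.206 = 0.577 points.

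**Why the direction varies.** A participant responds at 30% when the Week 8 score is below 0.7 × baseline. If the expected Week 8 score rises by *s* per baseline point, the margin for response changes by 0.7 − *s* per point. At 50% it is 0.5 − *s*, and at 70% it is 0.3 − *s*. So the effect of baseline shrinks and then reverses as the slope or the threshold rises.

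**Simulation at the 30% threshold (800 trials per setting, NRS category only).**

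| Slope *s* | 0.7 − *s* | Shift in risk difference per baseline point | × 0.577, percentage points | Variance ratio, without / with baseline |
|---|---|---|---|---|
| 0.2 | 0.5 | 0.051 | 2.9 | 1.10 |
| 0.4 | 0.3 | 0.032 | 1.8 | 1.02 |
| 0.6 | 0.1 | 0.009 | 0.5 | 0.98 |
| 0.8 | −0.1 | −0.003 | −0.2 | 0.99 |

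With baseline WOMAC in the model, the shift per point was within 0.006 of zero. A repeat gave about 0.04 per point at slope 0.2, that is 0.04 × 0.577 = 2.3 percentage points.

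**Other thresholds (same inputs, residual SD 3.3 assumed).** At 50% the shift per point ran from +0.021 to −0.025, with variance ratios 0.98 to 1.03. At 70% it ran from 0.00 to −0.023, with ratios 0.99 to 1.07. Multiplied by 0.577, these shifts are +1.2 to −1.4 and 0 to −1.3 percentage points.

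**Error rate and power.** A second simulation used 71 and 36 completers, baseline SD 3, Week 8 mean 8 and SD 4, baseline-to-Week 8 correlation 0.2 to 0.6, and 1,000 runs per setting.

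- With no drug effect, two-sided 5% rejection was 4.7% to 5.4% without baseline WOMAC and 4.5% to 5.9% with it. The Monte Carlo standard error is √(0.05 × 0.95 / 1000) = 0.7 points.
- With a 2-point effect, adding baseline changed power by −0.2 to +1.5 points (two-sided 0.05) or −0.7 to +3.1 points (one-sided 0.10).
- At correlation 0.2 the log odds ratio moved from 0.80 to 0.87 and its standard error from 0.43 to 0.45. The adjusted odds ratio is a conditional quantity, so the comparison should be brought back to marginal proportions.

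**The case against.** The best case for leaving the text alone is that nothing here threatens validity. Randomisation makes the comparison sound, and chance imbalance is already part of its sampling variance. These are other secondary endpoints in a proof-of-concept trial with no formal multiplicity adjustment. The continuous analyses of all three subscales already handle baseline properly. At the 30% threshold the SD of the estimated risk difference was about 0.10, so even a 3-point shift is about 0.3 SD. In several settings adjustment brought no gain in variance. All of this stands, and it sets the severity.

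It is also fair that the master SAP is not available and might add a baseline term. That limits the point to the supplied documents. It does not remove it, because Section 6.10.3 is specific and sends the reader to the key secondary list.

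Four stronger readings are tempting and are not supported:

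- *The responder analyses are biased or their error rate is inflated.* The null rejection rates show no inflation.
- *There is no adjustment for baseline severity.* The NRS category remains.
- *Precision is necessarily lost.* The variance ratio lies on both sides of 1.
- *All responder analyses are affected.* The NRS responder model is not shown here, and time to first response follows the master SAP.

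Nor does the OA01 schedule itself show baseline WOMAC collection; it lists WOMAC only at Visit 801 and refers to other schedules. Still, no percent reduction can be computed without a baseline score, so everyone who contributes a response has one.

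**Conclusion.** The point holds as a minor matter of specification and efficiency. As written, the WOMAC responder model has no baseline WOMAC term in the supplied documents, and it inherits a constraint that cannot apply to it. The numerical consequence is modest: 2 to 3 percentage points per SD of imbalance in the least favourable setting (30% threshold, weak dependence of Week 8 on baseline), and about nil or of opposite sign elsewhere. Variance without baseline is about 0.98 to 1.10 times that with it. These sizes rest on assumed means, SDs, correlations and drug effect, and on a single-visit logistic model in place of the planned repeated-measures one. The reading of Section 6.10.3 depends on none of them.

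**What to change.** In SAP Section 6.10.3, replace the cross-reference with an explicit list for the WOMAC responder models: treatment, visit, treatment-by-visit, baseline NRS category, pooled site, and the continuous baseline score of the same WOMAC subscale. State that response probabilities will be standardized over the observed covariates, so that the reported comparison remains a difference in proportions. If the master SAP already adds a baseline term, reconcile the two texts.

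No separate change is needed in Section 8 for the WOMAC responder analyses, which inherit the model. The NRS responder and time-to-first-response analyses should be left out of this edit.

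The cost is a short SAP edit, one extra parameter per model, and a marginalisation step in the programming.
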